10.2 Additional Secondary Endpoints

Patients will be evaluated for anti-tumor effect by follow-up imaging (lung protocol CT and/or PET-CT imaging) as outlined above. Lung protocol CT scans (biphasic imaging, 1.25 mm cuts) and/or FDG PET-CT scans will be obtained at all follow-up intervals as described in the treatment calendar. All subsequent scans (post-treatment) will be compared to the same pretreatment CT or PET/CT that was used in conjunction with radiation treatment planning.

Patients will be evaluated for objective response at the follow-up intervals specified above.

Response to SBRT will be assessed and reported according to RECIST Version 1.1 criteria.

Evaluation of Target Lesions (Primary Tumor)

Complete Response (CR): Disappearance of target lesion.

Partial Response (PR) : t least a 30% decrease in the diameter of target lesion, taking as reference the baseline diameter.

Progressive Disease (PD) : At least a 20% increase in the diameter of the target lesion, taking as reference the smallest diameter on study (this includes the baseline diameter if that is the smallest on study). In addition to the relative increase of 20%, the diameter must also demonstrate an absolute increase of at least 5 mm. (Note: the appearance of one or more new lesions is also considered progression).

Stable Disease (SD) : Neither sufficient shrinkage to qualify for PR nor sufficient increase to qualify for PD, taking as reference the smallest diameter while on study.

Failure will be documented by biopsy when possible and otherwise will be defined as radiologic progression on CT and/or PET/CT that leads to a change in management, including institution of systemic or local anti-cancer therapy. Failures will be categorized as follows:

Type of Recurrence	Description (after SABR treatment effects have subsided)
Local Failure	
Primary tumor failure (PTF)	Appearance of residual tumor located within the extent of the primary targeted tumor.
Marginal failure (MF)	Appearance of tumor ≤ 2 cm in any direction of the primary tumor or structures immediately adjacent to the primary tumor (lung/chest wall, mediastinum/diaphragm/spine).
Involved lobe failure (ILF)	Appearance of tumor > 2 cm in any direction of the primary tumor.
Regional Failure	
Non-primary lobe failure (NLF)	Appearance of tumor within another ipsilateral (non-primary) lobe.

Type of Recurrence	Description (after SABR treatment effects have subsided)
Hilar node failure (HNF)	Appearance of tumor in ipsilateral hilar lymph nodes.
Ipsilateral mediastinal nodal failure (MNF)	Appearance of tumor in ipsilateral mediastinal and/or subcarinal lymph nodes.
Distant Failure	
Distant nodal failure (DNF)	Appearance of tumor in ipsilateral supraclavicular or contralateral lymph nodes.
Distant metastatic failure (DMF)	Appearance of tumor deposits characteristic of NSCLC metastasis (chest wall other than incision sites or immediately adjacent to primary, mediastinal structures/diaphragm, malignant pleural effusion/pericardial effusion), contralateral lung and/or other distant sites.

Potential adverse events will be monitored by treating physicians at each follow-up visit, and scored using CTCAE v4 with type and grade.

Post-treatment changes in pulmonary function will be evaluated by changes in pulmonary function test at enrollment, 6-month, and 12-month follow-up.

Recurrence rate is determined by time from study enrollment to first documented date of recurrence.

Progression-free survival (PFS) is time from time from study enrollment until the first documented date of disease progression.

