8. Uncontrolled, inter-current or recent illness that in the investigator's opinion precludes participation in the study, including those undergoing therapy for a separate invasive malignancy
9. Contraindication to receiving radiotherapy
10. Known allergy to components of fresolimumab
11. Pregnant or breastfeeding. All women of child-bearing potential (last menstrual period within the previous 12 months and not surgically sterile) will be tested for pregnancy at pre-entry.

Intervention and Mode of Delivery:

Phase 1 component:

Fresolimumab will be administered intravenously (IV) at a dose of 3 mg/kg on Days 1, 15, and 36 and SABR will be administered at 12.5 Gy/fraction in 4 fractions between Days 8 and 12 to a total of 5 patients who will be evaluated for safety, and additional patients will be enrolled if specific AE's are observed. A dose reduction may be implemented if excessive toxicity is observed.

Phase 2 component:

Fresolimumab will be administered IV at the dose selected in the preceding Phase 1 component (3 mg/Kg) on Days 1, 15 (+ 6 days), and 36 (+/- 6 days) and SABR (-1/+5 days) will be administered at 12.5 Gy/fraction in 4 fractions between Days 8 and 12.

Duration of Intervention and Evaluation: The study duration will be approximately 6 years (5 years for accrual and 1 year for follow-up)

Statistical Methods:

Definition of primary outcome/endpoint:

Phase 1:

DLT is defined as CTCAE grade 3 or higher radiation pneumonitis or bronchopulmonary hemorrhage

Phase 2:

Presence of radiation-induced pulmonary fibrosis is defined as presence of a moderate-to-severe level of fibrosis in each patient by 12 months

Definition of secondary outcomes/endpoints:

Phase 1:

- Potential adverse events is defined by CTCAE v4
- Post-treatment changes in pulmonary function will be evaluated by changes in pulmonary function test at enrollment, 6-month, and 12-month follow-up
- Recurrence is defined as presence of local, regional, and/or distant recurrence by 12 month
- Progression-free survival is time from time from study enrollment until the first documented date of disease progression.
- Extent of radiation-induced lung toxicity is morphological changes on CT and PET after treatment
- Presence of radiation induced pulmonary fibrosis is defined as presence of a moderate-to-severe level of fibrosis in each patient by 12 months
- Severity of radiation induced pulmonary fibrosis is degree of fibrosis after SABR

Phase 2:

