2.2 Study Agent/Device/Procedure

Stereotactic Ablative Radiotherapy

In non-operable NSCLC patients, stereotactic ablative radiotherapy (SABR), also called stereotactic body radiation therapy (SBRT), has recently emerged as an important treatment option [3, 4]. A landmark prospective phase 2 clinical trial conducted by the Radiation Therapy Oncology Group, RTOG 0236, found that SABR resulted in outstanding local control (LC) and overall survival (OS) rates of 98% and 56% at 3 years in a cohort of strictly medically inoperable patients with peripherally located stage I NSCLC [5]. While extremely well tolerated, SABR almost always produces a significant fibrotic reaction in the targeted region of the lung. These fibrotic reactions result in loss of function of the affected lung tissue and significantly complicate detection of post-SABR recurrences.

Transforming growth factor-beta

Transforming growth factor-beta (TGF β) is a pleiotropic cytokine expressed as three isoforms; TGF β 1, TGF β 2, and TGF β 3 and belongs to a superfamily of ligands comprised of more than 30 proteins such as bone morphogenetic proteins, activins, and inhibin. TGF β isoforms are involved in a number of normal biologic and physiologic processes such as cell proliferation, cell differentiation, cell motility, apoptosis, angiogenesis, and extracellular matrix production [6]. In normal non-cancerous cells TGF β limits the growth of epithelial, endothelial, neuronal, and

hematopoietic cells through induction of anti-proliferative and apoptotic responses but in cancer TGF β has been shown to have growth promoting and prometastatic effects [7, 8].

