12.4 Primary and Secondary Endpoints

Phase 1:

Primary Endpoint

- Dose limiting toxicities (DLTs) of fresolimumab when combined with SABR

Secondary Endpoint

- Score the pattern of late radiation induced fibrosis at 12 months after SABR with and without fresolimumab
- Evaluate severity and pattern of acute radiation-induced fibrosis in the first 6 months after SABR
- Score potential adverse events (AEs) of fresolimumab combined with SABR using CTCAE v4
- Measure post-treatment changes in pulmonary function using pulmonary function test parameters at enrollment, 6-month, and 12-month follow-up
- Evaluate recurrence and progression-free survival at 12 months
- Measure blood pharmacokinetics (PK) of fresolimumab in combination with SABR (optional for patient)

Exploratory Endpoint:

- Assess extent of radiation-induced lung toxicity by quantitative imaging analysis of CT volumes and FDG uptake parameters

Phase 2

Primary Endpoint

Evaluate the presence of late moderate-to-severe radiation-induced fibrosis up to 12 months after SABR with fresolimumab

Secondary Endpoint

- Score the pattern of late radiation induced fibrosis at 12 months after SABR with and without fresolimumab
- Evaluate severity and pattern of acute radiation-induced fibrosis in the first 6 months after SABR
- Score potential adverse events (AEs) of fresolimumab combined with SABR using CTCAE v4
- Measure post-treatment changes in pulmonary function using pulmonary function test parameters at enrollment, 6-month, and 12-month follow-up
- Evaluate recurrence and progression-free survival at 12 months

Exploratory Endpoint:

- Assess extent of radiation-induced lung toxicity by quantitative imaging analysis of CT volumes and FDG uptake parameters

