12.4.1 Analysis Population

Analysis will be carried out in all patients who complete protocol procedures. Patients who are lost to follow-up and who do not have a scan within +/-6 months of the 12-month time point will be excluded from analysis. Patients who develop inflammatory lung conditions unrelated to radiotherapy (i.e. pneumonia, ARDS, drug-induced pneumonitis, etc.) will be excluded from the final endpoint analysis if the area of unrelated inflammation impedes scoring of fibrosis severity of the irradiated lesion.

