12.4.2. Analysis Plan

Approximately 60% of SABR patients develop acute radiologic changes in the lung at 3 months [16]. Late radiologic changes, reflecting fibrosis, are more frequent in SABR patients at 1 year [15]. Our institutional experience revealed the presence of moderate-to-severe late radiation induced fibrosis in ~75% of patients treated with SABR (50 Gy in 4 fractions) via VMAT technique at 1 year.

Primary analysis: The outcome of moderate-to-severe radiologic fibrosis rate will be tested in evaluable patients in a one-sample one-sided test of proportion comparing the observed rate, which is expected to be at most 58%, to the historically observed rate of ~75%. The observed rate and the 95% confidence interval calculated using the exact method will be reported.

Secondary analysis: Local control at 12 months will be estimated along with a one-sided lower 95% confidence bound to allow an informal assessment of the null hypothesis that the proportion is larger than 80%. Patients with distant progression before local failure will be censored one day after the last imaging study; patients who die before local control will be censored at the time of death. These definitions are used for comparability. Cumulative incidence estimates for local failure and other failure type will also be presented.

Time to event data (local control, PFS, time to progression) will be evaluated using Kaplan-Meier estimates with 95% confidence intervals at multiples of 12 months based on Greenwood's formula with a log transform. Confidence intervals for median times to event, if relevant, will be constructed using the method of Brookmeyer and Crowley.

Proportions (eg, proportion of patients with grade 4 or higher toxicity) will be estimated along with 95% exact confidence intervals. Patient clinical and demographic characteristics will be reported with the appropriate summary statistic (mean, range, proportion, etc.) Adverse events will be tabulated by organ system and severity.

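### Progression-free survival is defined without death as an event, so as written it is time to progression and would overstate 12-month PFS for each patient who dies without progression

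*Combined protocol and SAP*

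**What the plan says.** PFS at 12 months is a secondary endpoint in both phases. Section 12.4 lists it as "Evaluate recurrence and progression-free survival at 12 months".

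It is defined twice, in the same terms:

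- Section 10.2: "Progression-free survival (PFS) is time from time from study enrollment until the first documented date of disease progression".
- Synopsis, definitions of secondary outcomes: "Progression-free survival is time from time from study enrollment until the first documented date of disease progression".

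The synopsis's analytic plan adds that PFS is read from the follow-up imaging, up to one year.

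Section 12.4.2 names the estimator and places PFS beside a separate variable: "Time to event data (local control, PFS, time to progression) will be evaluated using Kaplan-Meier estimates". Its only rule for deaths belongs to local control: "patients who die before local control will be censored at the time of death". Section 12.4.1 opens with a general restriction: "Analysis will be carried out in all patients who complete protocol procedures".

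**The concern.** PFS conventionally fails at progression or at death, whichever comes first, and a reader will take the 12-month figure as the share of patients alive without progression. The written rule gives the share without documented progression. The two differ as soon as one patient dies first, and the written version is always the more favourable.

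Eligibility covers patients who are inoperable or at high surgical risk, so deaths from other causes within a year are plausible. Overall survival is not among the endpoints in section 12.4, so PFS is the listed endpoint whose name promises to count deaths.

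The definition also conflicts with the plan's own list of variables. Section 12.4.2 treats PFS and time to progression as two quantities, but the PFS definition leaves nothing to separate them.

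**Working it through.** The documents state no PFS rate, event count or PFS-based sample size, so there is no figure to reproduce. The check has two parts.

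**1. Does any section make death a PFS event?**

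- Synopsis and section 10.2: the endpoint is progression only.
- Synopsis, analytic plan: ascertainment is by imaging. A death without progression produces no imaging event.
- Section 4.2.5 names progression and death together, but as reasons to stop study treatment.
- Section 12.4.2: deaths are censored, for local control only. Nothing is said for PFS.

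No section does. With Kaplan-Meier specified and death not an event, the ordinary handling is to censor at death.

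**2. How large is the effect?**

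Assumed for illustration: N = 50, 5 progressions by 12 months, k deaths without progression by 12 months, no other losses.

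- Death as an event: PFS = (50 − 5 − k)/50.
- Deaths censored: the Kaplan-Meier estimate depends on the order of events. It is lowest when all deaths come first, (45 − k)/(50 − k), and highest when all come last, 45/50.

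| k | Death as event | Deaths censored | Excess, points |
|---|---|---|---|
| 0 | 45/50 = 90.0% | 90.0% | 0 |
| 1 | 44/50 = 88.0% | 44/49 = 89.8% to 90.0% | 1.8 to 2.0 |
| 3 | 42/50 = 84.0% | 42/47 = 89.4% to 90.0% | 5.4 to 6.0 |
| 5 | 40/50 = 80.0% | 40/45 = 88.9% to 90.0% | 8.9 to 10.0 |

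Enumerating all 56 orderings for k = 3 confirms the limits of 89.4% and 90.0%. In each row the excess is 1.8 to 2.0 points per death.

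**A loose outer guide.** The documents give no 12-month death rate for this trial. The only survival figures are from a cited phase 2 SABR trial, in section 2.2: local control and "overall survival (OS) rates of 98% and 56% at 3 years in a cohort of strictly medically inoperable patients". Under an assumed constant hazard, 12-month all-cause mortality is 1 − 0.56^(1/3) = 17.6%, or 8.8 of 50.

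Assume one quarter to three quarters of those deaths occur without progression. The proportion d is then 0.0439 to 0.1318, or 2.2 to 6.6 of 50. Assume also that a proportion p of 5% to 20% progress by 12 months. With constant hazards, true PFS is 1 − p − d and the censored Kaplan-Meier estimate is (1 − p − d)^(p/(p + d)).

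- Smallest excess (d = 0.0439, p = 0.20): 0.7561^0.8199 = 0.7951; 0.7951 − 0.7561 = 3.9 points.
- Largest excess (d = 0.1318, p = 0.05): 0.8182^0.2750 = 0.9463; 0.9463 − 0.8182 = 12.8 points.

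**The case against.** **Conventional PFS was obviously meant.** Listing time to progression separately does suggest this. But intent does not repair a definition given twice in the same terms, and an analyst who follows the text would not count deaths. What stands is that the overstatement is conditional: it needs the definition to be applied as written and at least one death without progression by 12 months.

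**Section 12.4.1 might drop patients who die early.** A reader might infer this from the completer sentence. The documents do not support building on it. The specific exclusions that follow concern the 12-month scan and the scoring of fibrosis, and section 12.4.2 censors patients at death for local control, which makes sense only if they remain in the time-to-event analyses. Nor does any text suggest keeping dead patients in the risk set. Censoring is the reading that fits, and the sizes above use it alone.

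**PFS might seem to duplicate the recurrence endpoint.** Section 10.2 says "Recurrence rate is determined by time from study enrollment to first documented date of recurrence", which has the same form. But that section defines failure by biopsy, or by radiologic progression that changes management, while progressive disease follows RECIST. The two can differ without any death, so the resemblance proves little.

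**The outer guide stacks assumptions.** This is fair. It takes a constant hazard from another trial in strictly inoperable patients, whereas this trial also admits patients who refuse surgery. The share of deaths without progression is assumed too.

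**PFS carries no test, threshold or decision rule.** This is true, and it limits the importance of the point.

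**Conclusion.** The point holds as a defect of definition. Both statements of PFS omit death, nothing elsewhere supplies it, and what would be reported under the PFS label is time to progression.

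The firmest size is roughly 2 points per death without progression by 12 months in 50 patients; it rests on the assumed 5 progressions and on censoring. The total cannot be derived from the documents. The 3.9 to 12.8 points is an illustration under stacked assumptions, not a forecast.

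A reader might infer that 12-month PFS is certain to be overstated. The documents do not support that: with no death before progression there is no excess. A reader might also infer that the main result is compromised. It is not. The Phase 2 fibrosis test and its sample size of 50 do not use PFS. The correction is worth making because it is cheap and the reported figure would otherwise be misread.

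**What to change.** - **Synopsis and section 10.2:** define PFS as time from enrollment to first documented progression or death from any cause, whichever comes first. Censor patients alive without progression at their last evaluable imaging. PFS then differs from the time to progression in section 12.4.2.
- **Section 12.4.1:** state that the completer restriction and the fibrosis-scan exclusions do not apply to PFS. Use an analysis set that fits the time origin: all enrolled patients, or, if only treated patients are analysed, move the origin to first treatment.
- **Data capture:** confirm that the case report form records date of death through 12 months. Section 12.4.2 already needs death dates to censor local control. However, routine adverse event collection in section 7.3 ends 30 days after the last study treatment, the study calendar has no separate vital-status contact, and follow-up after stopping treatment is only as feasible (section 4.2.5).

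The cost is a few lines of text and some work to establish vital status after missed visits. No new scans or visits are needed. Reported PFS may be less favourable, and its analysis set will differ from that of the fibrosis endpoint, which the report must state.

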11. REGULATORY CONSIDERATIONS

11.1 Institutional Review of Protocol

The protocol; the proposed informed consent; and all forms of participant information related to the study (eg, advertisements used to recruit participants) will be reviewed and approved by the Stanford IRB and Stanford Cancer Institute Scientific Review Committee (SRC). Any changes made to the protocol will be submitted as a modification and will be approved by the IRB prior to implementation. The Protocol Director will disseminate the protocol amendment information to all participating investigators.

11.2 Data and Safety Monitoring Plan

The Stanford Cancer Institute Data and Safety Monitoring Committee (DSMC) will be the monitoring entity for this study. The DSMC will audit study-related activities to determine whether the study has been conducted in accordance with the protocol, local standard operating procedures, FDA regulations, and Good Clinical Practice (GCP). This may include review of the following types of documents participating in the study: regulatory binders, case report forms, eligibility checklists, and source documents. In addition, the DSMC will regularly review serious adverse events and protocol deviations associated with the research to ensure the protection of human subjects. Results of the DSMC audit will be communicated to the IRB and the appropriate regulatory authorities at the time of continuing review, or in an expedited fashion, as needed.

11.3 Data Management Plan

The Protocol Director, or his/her designee, will prepare and maintain adequate and accurate participant case histories with observations and data pertinent to the study. Study-specific Case Report Forms (CRFs) will document treatment outcomes for data analysis. Case report forms will be developed using REDCap database system and will be maintained by the Clinical Research Coordinator assigned to this study. CRFs will be kept in a locked cabinet, only accessible to the research team.

12. STATISTICAL CONSIDERATIONS

12.1 Statistical Design

[name] (Biostatistician at Stanford University) is the statistician for this study.

12.1.1 Randomization

This is a non-randomized study.

12.2 Interim analyses

A review of the safety data will be completed every 6 months at the weekly Thoracic Radiation Oncology Team Meetings.

12.3 Descriptive Statistics and Exploratory Data Analysis

See section 12.4.2.

12.4 Primary and Secondary Endpoints

Phase 1:

Primary Endpoint

- Dose limiting toxicities (DLTs) of fresolimumab when combined with SABR

Secondary Endpoint

- Score the pattern of late radiation induced fibrosis at 12 months after SABR with and without fresolimumab
- Evaluate severity and pattern of acute radiation-induced fibrosis in the first 6 months after SABR
- Score potential adverse events (AEs) of fresolimumab combined with SABR using CTCAE v4
- Measure post-treatment changes in pulmonary function using pulmonary function test parameters at enrollment, 6-month, and 12-month follow-up
- Evaluate recurrence and progression-free survival at 12 months
- Measure blood pharmacokinetics (PK) of fresolimumab in combination with SABR (optional for patient)

Exploratory Endpoint:

- Assess extent of radiation-induced lung toxicity by quantitative imaging analysis of CT volumes and FDG uptake parameters

Phase 2

Primary Endpoint

Evaluate the presence of late moderate-to-severe radiation-induced fibrosis up to 12 months after SABR with fresolimumab

Secondary Endpoint

- Score the pattern of late radiation induced fibrosis at 12 months after SABR with and without fresolimumab
- Evaluate severity and pattern of acute radiation-induced fibrosis in the first 6 months after SABR
- Score potential adverse events (AEs) of fresolimumab combined with SABR using CTCAE v4
- Measure post-treatment changes in pulmonary function using pulmonary function test parameters at enrollment, 6-month, and 12-month follow-up
- Evaluate recurrence and progression-free survival at 12 months

Exploratory Endpoint:

- Assess extent of radiation-induced lung toxicity by quantitative imaging analysis of CT volumes and FDG uptake parameters

